Aim 2 (Part 2, subjects 3-6): Test an additional 4 subjects according to the results of Part 1. **Hypothesis 2:** *Additional subjects treated at the same dose will refine the statistical confidence in the observations of Objective 1.*

Aim 3 (Part 3, subjects 7-12): Using the final targeted dose of drug, study 6 subjects using the same in-patient protocol as in the other aims. **Hypothesis 3:** *Using the final dosing scheme, the last six subjects will demonstrate a significant reduction in fasting and stimulated lipogenesis, with the lowest side effects, if any.*

Study Details

The sources of research materials will include following items.

Screening: Research subject and family medical history, demographic data, vitals, height, weight, BMI calculated, and screening laboratory tests including a CMP, hepatitis panel, CBC with differential, concentration of insulin, a lipid panel, apolipoproteins B and A1, ECG, and HbA1c. Demographic data (plus other related data, e.g., emergency contact person), smoking history are collected, along with lifestyle information including food/beverage/alcohol intake and physical activity will be obtained via questionnaire and a urine sample is used for a general drug screen.

Inpatient CRC studies: Blood is processed to obtain plasma and the sample used in the isolation and measurement of blood metabolites and hormones including glucose, fructose, TG, FFA, ketones, insulin, and for the VLDL-lipoproteins, apolipoprotein B100, VLDL-TG concentration, and TG-palmitate lipogenesis. Once the samples have been processed for mass spectrometry and the data acquired, the processed samples will be kept until at least 10 years after publication (the stable isotope does not decay and the samples retain their value). DEXA is used to measure total and regional fat mass and fat-free mass, a FibroScan® ultrasound is performed to measure liver elastography (liver stiffness due to fibrosis), and MRI is used to assess liver fat. Indirect calorimetry is performed to measure energy expenditure, and skin oil collected (Sebutape®) to measure fatty acid composition. **Table 1** shows how the timeframe over which the 324 ml of blood is donated by the subject.

Table 1. Accounting of Blood Usage

Procedure	Volume of whole blood (mls)
Screening blood chemistries	40
V1. Baseline inpatient study	100
V2. D4 safety blood draw	10
V3. D6 safety blood draw	10
V4. D9 safety blood draw	14
V5. Follow-up inpatient study	140
V6. Follow-up safety blood draw	10

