Total for 12 subjects (mls)	324

Schedule of Events

Telephone Screening: The subject will respond to the recruiting flyer or advertisement and answer the waiver of written consent and screening questions. These questions are for preliminary screening only and are not used as study data since the data represent self-report. The questions include queries about health history/habits, age, gender, height, weight, tobacco use, medications/supplements, over-the-counter drugs use, illness, and chronic conditions. The study design is described in general terms to subjects, with mention of three factors most likely to impact subject interest in participating. These factors include having an IV line, that there are two overnight stays in a hospital research unit, and that the drugs may have side effects. If the subject is interested in being screened for participation, research staff then makes an appointment for the subject to come into the CRC for formal consenting, and screening procedures. The length between the screening visit and beginning study procedures may vary according to subject's availability but will not be longer than 4 weeks. For each of the visits shown in **Figure 1**, the procedures as are described below.

Screening and Consenting Visit: The first visit to the CRC will include a written formal consent. We estimate that we will have to screen 100 people to find the 12 subjects to do the study. After signing the consent form, medical information is obtained by the nurse including DOB, gender, ethnic/racial category, height, body weight (history of body weight), vitals, and medical history (medications use, smoking history and a fasting blood draw (40 mL) is taken to test for biochemistries). An ECG will be performed and read by [name], Cardiology.

As soon as the blood biochemistry results are available, the subject is contacted, provided with a copy of the results, told whether he is eligible to continue, and asked if they want to participate further. Staff also ask the subject to describe, in their own words, what the baseline visit will be like. If they agree to participate, an appointment is made for the subject to come to the CRC for their overnight baseline visit.

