Safety Blood Draw Visit 6: Approximately 5-7 days following visit 5, the subject will come into the CRC for a final safety blood draw. The subject is asked to not exercise on this morning before this blood draw. For 12 hours before he comes to the visit, the subject is told to not eat or drink anything besides water. A small amount of blood will be taken (10 mls). This visit will take about 30 minutes.

Human Subjects Involvement and Characteristics

Recruitment and informed consent: The study population includes overweight and obese male subjects, aged 35-60y. The recruitment process will include the typical flyers and notices put in public spaces. The recruitment material will be posted around University of Missouri campus, as well as other public places such as swimming pools, churches, and grocery stores. We also plan to use the service called Studykik (<https://studykik.com/>). All advertisements will state the purpose of the study, eligibility criteria and will tell subjects to call into our laboratory for more information. During these calls, the study will be described briefly. A checklist will be phone through to perform initial screening for age, gender, health status. Subjects who are eligible by phone screen will be scheduled for a screening visit.

The consent form states the purpose of the study, risks, inconveniences, discomforts, and other important information about the study and has been prepared in lay terms so that it is easy to understand. During the screening visit the form is reviewed comprehensively. The subject will be instructed to ask questions about any words or information that they do not clearly understand and questions will be answered by the PI and her staff. This will enable us to determine the subject's comprehension of the study. The consent form will be signed before any study procedures are initiated.

Criteria for inclusion

1. Men with characteristics of metabolic syndrome
 - a) Waist circumference greater than 40 in (102 cm)
 - b) Plasma TG greater than 150 mg/dL
 - c) HDL cholesterol less than 40 mg/dL
 - d) Blood pressure greater than or equal to 130/85 mmHg
 - e) Fasting plasma glucose greater than 100 mg/dL but less than 126 mg/dL
 - f) Fasting insulin great than 10 uU/mL
2. 35-60 years of age
3. Overweight/obese subjects with BMI 27.1 - 45.0 kg/m²
4. Family history of CVD or diabetes
5. Habitual diets containing $\geq 5.0\%$ of energy from added sugars
6. Creatinine clearance of ≥ 80 mL/min

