Criteria for exclusion

1. Diagnosed CVD (unstable angina, NYHA angina > Grade 2), abnormal thyroid function or liver/kidney disease, renal dysfunction (defined by GFR <80 mL/min)
2. Signs of ascites and signs of hepatic encephalopathy (a score greater than 7 on the Child-Pugh scale, that would place them in either class B or C)
3. Chronic skin disorder or treatment for acne
4. History of clinically significant dry eye or eye diseases such as glaucoma
5. Diabetes defined as fasting glucose ≥ 125 mg/dL or HbA1c $\geq 6.5\%$
6. Habitual diets with low content of added sugars (<5% of total energy)
7. Any tobacco use
8. Elevated liver enzymes $\geq 3x$ normal (regional norms ALT <42 U/L, AST <40 U/L, and GGT 8-61 U/L) and extended prothrombin time (PT >11.5 seconds)
9. Contraindications of MRI
10. Alcohol intake weekly greater than 56 g/week (4 standard drinks/wk).
11. Major surgery or donation of blood of >500 mL within the past 8 wks.
12. Patients with uncontrolled hypertension, i.e. $\geq 160/95$ mmHg.
13. Patients with known cardiac abnormalities such as:
 - Congenital long QT syndrome
 - QTc interval > 480 milliseconds
 - Any cardiac arrhythmia requiring anti-arrhythmic medication.
14. Patients who have had a myocardial infarction within 12 months of study entry.
15. Patients who have a history of coronary artery disease (CAD) e.g. angina Canadian class II to IV [10]. In any subject in whom there is doubt, the subject will be excluded.
16. Patients with an ECG recorded at screening showing evidence of cardiac ischemia (ST depression of ≥ 2 mm). If in any doubt, the patient should have a stress imaging study and exercise ECG and, if abnormal, angiography to define whether or not CAD is present.
17. Patients with congestive heart failure that meets New York Heart Association class II to IV definitions and/or ejection fraction <40% by multiple gated acquisition (MUGA) scan or <50% by echocardiogram and/or magnetic resonance imaging (MRI)
18. Patients with a history of sustained ventricular tachycardia (VT), ventricular fibrillation (VF), Torsade de Pointes, or cardiac arrest, unless currently addressed with an automatic implantable cardioverter defibrillator (AICD).

19. Patients with hypertrophic cardiomegaly or restrictive cardiomyopathy from prior treatment or other causes (if in doubt, see ejection fraction criteria above).
20. Patients with a history of pneumonitis.

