21. Individuals taking drugs that are substrates for CYP3A or CYP2C9 and have a narrow therapeutic index. Examples of these drugs include statins (atorvastatin, simvastatin), diuretics (conivaptan, naloxego, eplerenone, tolvaptan), anti-hypertensives (nisoldipine, felodipine), anti-inflammatories (celecoxib, ebastine), narcotics and sedatives (alfentanil, midazolam, triazolam), antipsychotics (buspirone, lurasidone, quetiapine), other lipid-lowering agents (lomitapide) and erectile dysfunction medications (avanafil, vardenafil, sildenafil). Other drugs that would make potential subjects ineligible include HIV anti-retrovirals, immunosuppressants and chemotherapeutic agents.
22. Individuals who are taking drugs that are strong inhibitors or reducers of CYP3A. Examples of these drugs include, diuretics (conivaptan), antifungals agents and antibiotics (rifampin, itraconazole, ketoconazole, troleandomycin, voriconazole, clarithromycin), antidepressants (nefazodone, St. Johns Wort) and antihypertensives (diltiazem).

Subject compensation

Subjects will be compensated based on the amount of their participation in the study as follows:

- \$150.00 for consuming the 3 day pretest diet and for baseline visit 1
 - \$75.00 for participating in safety blood draw visit 2
 - \$100.00 for participating in safety blood draw visit 3
 - \$150.00 for participating in safety blood draw visit 4
 - \$225.00 for consuming the 10-day diet and for participating in follow up visit 5
 - \$500.00 for participating in safety blood draw visit 6
- Thus, if subjects complete the study, they will be compensated a total of \$1,200.00.

Subjects who live 1-2 hours away from Columbia by car will be reimbursed \$25 for the screening visit.

Potential risks

Physical risks may include:

1. Intravenous catheterization: The tests in the present protocol require one IV line to be in for roughly 24 hrs and another to be in for roughly 8 hrs. The standard rule of thumb for hospital infection control is for an IV line to be replaced every 48 hrs. The duration of the IVs in the present protocol is less than this time. Placement of IV lines may cause bleeding, bruising, infection, clotting, pain at the needle site, and/or fainting. Extravasation of study substances could cause swelling and local irritation at the intravenous site. A black and blue mark may result from placement of an IV. This can be painful, but it carries no significant risks. Infections from IVs rarely occur.

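### Does the wording of exclusion 8 (liver enzymes 'and' prothrombin time), with two glucose cut-offs 1 mg/dL apart, leave eligibility undefined?

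*Combined protocol and SAP*

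**What the plan says.** Exclusion 8 (Criteria for exclusion) is a single item. It names liver enzymes at or above three times normal, gives regional norms of ALT below 42, AST below 40 and GGT 8 to 61 U/L, and then adds "and extended prothrombin time (PT >11.5 seconds".

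The Screening paragraph of Study Details lists "screening laboratory tests including a CMP, hepatitis panel, CBC with differential, concentration of insulin, a lipid panel, apolipoproteins B and A1, ECG, and HbA1c". The Screening and Consenting Visit paragraph says only that "a fasting blood draw (40 mL) is taken to test for biochemistries". PT and GGT appear nowhere outside exclusion 8.

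On glucose, inclusion 1e reads "Fasting plasma glucose greater than 100 mg/dL but less than 126 mg/dL". Exclusion 5 defines diabetes as fasting glucose at or above "125 mg/dL or HbA1c" at or above 6.5%.

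Under Subject safety procedures, eligibility is determined by two named doctors in consultation with a third person, and on-study chemistry results are sent for review. Exclusion 1 separately excludes liver disease, without a numeric limit.

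**The concern.** Item 8 holds the protocol's only numeric limit on liver enzymes. If its conjunction can be read two ways, the same man could be accepted under one reading and refused under the other. Other items do not remove all doubt. Item 2, "Signs of ascites and signs of hepatic encephalopathy", joins two findings in a way that looks like a loose list, so the authors may have meant item 8 loosely too. A criterion that relies on PT and GGT also seems hard to apply when the screening paragraph names neither.

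The glucose limits look like a contradiction: inclusion 1e admits 125 mg/dL and exclusion 5 refuses it. Another mirrored pair agrees exactly: exclusion 6, "Habitual diets with low content of added sugars (<5% of total energy"), is the complement of inclusion 5 at 5%. That makes the glucose pair look like a drafting mismatch.

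At stake is whether every candidate is judged by the same rule. The within-subject lipogenesis estimate is not in question.

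**Working it through.** **1. Exclusion 8 under each reading.** Three times the upper norms stated in the item gives:

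- ALT: 3 × 42 = 126 U/L
- AST: 3 × 40 = 120 U/L
- GGT: 3 × 61 = 183 U/L

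| Enzymes at limit | PT above 11.5 s | Both required | Either suffices |
|---|---|---|---|
| no | no | not excluded | not excluded |
| no | yes | not excluded | excluded |
| yes | no | not excluded | excluded |
| yes | yes | excluded | excluded |

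The readings differ in two of the four rows. These decisions are under item 8 alone; a man in the third row may still be excluded under item 1. The item also does not say whether one raised enzyme is enough or all three are needed, so the three limits do not define the affected group without a further assumption. The documents give no enzyme or PT distribution, so the number of men in the two middle rows cannot be estimated.

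**2. What the list's own usage implies.** Items 3, 4, 5, 11 and 19 write *or* where either state excludes. Item 17 writes *and/or*. Item 21 uses *and* where both conditions must hold: "substrates for CYP3A or CYP2C9 and have a narrow therapeutic index". All of this favours the literal reading of item 8. The one counter-example is item 2, and it is weak, because a parenthesis ties its two signs to a single Child-Pugh score.

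**3. Screening tests.** The list is introduced by *including*, so it is not exhaustive. It also names panels rather than analytes: glucose, creatinine, ALT and AST are not listed individually either, although criteria depend on them. Table 1 allots 40 mL to screening blood chemistries. The text therefore supports 'not named'; it does not support 'not measured'.

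**4. Glucose.** In whole numbers:

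- Inclusion 1e (above 100, below 126) covers 101 to 125: 125 − 101 + 1 = 25 values.
- Exclusion 5 (125 or above) removes 125, leaving 101 to 124: 24 values.
- Overlap: 25 − 24 = 1 value; the cut-offs differ by 126 − 125 = 1 mg/dL.

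Inclusion 1 lists a) to f) as characteristics of metabolic syndrome without saying that all are required. If 1e must be met, the admissible whole-number range is 101 to 124. If it need not be met, the upper bound comes from exclusion 5 alone and is still 124. A man at 125 is out either way, provided that meeting an exclusion rules a candidate out, which is the ordinary meaning of the list.

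**5. Link to the analysis.** Each subject is his own control, and the Statistical analysis section names a paired t-test. The reading of item 8 can change which men enter; it does not enter the calculation of a man's baseline-to-follow-up difference, and it leaves the sample-size figures unchanged.

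**The case for a change.** The strongest case for acting is that liver eligibility is not peripheral here. The drug targets hepatic lipogenesis, the Background calls obesity and metabolic syndrome key risk factors for fatty liver disease, and about 100 people are expected to be screened for 12 places, so item 8 will be applied many times. The safeguards do not interpret it: exclusion 1 has no enzyme threshold, the doctors apply the criteria without being told how to read this one, and on-study chemistries come after entry. Clarifying would cost a sentence and at most two assays on blood already drawn.

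Part of this stands. Item 2 leaves some doubt about intent, the item does not say how many enzymes must be raised, and a clarifying sentence would do no harm.

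The rest does not make it a defect in the plan. Inconsistent decisions are mainly a risk where assessors work separately; here a small group at one centre decides in consultation and can settle the reading once. The side effects reported in the Background and under Potential risks include no liver toxicity, so no known hazard is shown to be missed. No test is shown to be unmeasured, and the glucose mismatch admits no one improperly. The low cost of an edit does not show that it would gain anything for the trial's conclusions.

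**Conclusion.** No change to the plan is called for. Item 8 has a literal meaning, that both findings are required, and most of the surrounding list supports it. Whether the authors intended that meaning, and whether one raised enzyme is enough, are details for the sponsor and investigators to confirm; no view is taken here on which clinical rule is right. The unnamed PT and GGT are missing detail in an open-ended list. The glucose pair is a clerical slip of 1 mg/dL that affects one whole-number value and can be reconciled whenever the text is next edited.

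The item 8 point covers two of four enzyme/PT combinations, with an unknown number of candidates in them. The conclusion assumes that exclusions override inclusions, that the screening draw can include assays not named in the list, and that the doctors named for eligibility apply one reading to all candidates. If the last assumption failed, the mix of men enrolled could shift slightly, but each man's change from baseline would still be measured against himself.
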